Pregnant women are a priority group for the receipt of the seasonal inactivated influenza vaccine because of: i) the increased risk of adverse outcomes to themselves and their fetuses should they become ill with influenza, and ii) the need to protect infants during a period when they are too young to receive the vaccine themselves. Although the seasonal inactivated influenza vaccine has been shown to be safe and well tolerated in the second and third trimesters of pregnancy, little data exist on the outcomes of vaccination during the first weeks of pregnancy. If adverse outcomes occur, then this may be tied to hormonal changes that are secondary to inflammatory cytokine responses following vaccination. During a healthy pregnancy, steroid hormones, including estradiol, progesterone, and cortisol increase substantially and contribute to reductions in inflammatory cytokine concentrations that are necessary to support a successful pregnancy [1-3]. Through the mechanisms of bidirectional communication between endocrine and immune cells, questions arise as to whether activation of immune cells by infection or vaccination and the subsequent production of inflammatory cytokines, including TNF- α , could change steroid hormone concentrations and the outcome of pregnancy [4]. This open label prospective trial expands our pilot study conducted during the 2013-2014 influenza season in which we examined the effect of seasonal inactivated influenza vaccine (IIV) on inflammatory cytokines and hormonal responses in healthy women of reproductive age. Our initial findings showed a non-significant 20% decrease in serum progesterone vaccination as compared to the same menstrual cycle time point (day 17) in the non-vaccinated month[5]. Initial findings also showed increases in some cytokine levels after vaccination [5]. With the additional participants provided by this amendment, we would like to repeat our initial pilot study during 1 or 2 additional influenza seasons with some modifications, in order to better understand the early responses to influenza vaccine and the effects on hormones. The women will be recruited at the Center for Immunization Research, Johns Hopkins Bloomberg School of Public Health, followed for one menstrual cycle to measure estradiol, progesterone, and cytokines and then vaccinated with the seasonal inactivated influenza vaccine prior to ovulation during a second month. At the investigator's discretion, or if there is active circulation of influenza virus in Baltimore, we will vaccinate during the first menstrual cycle (prior to ovulation) and then follow for a second menstrual cycle for comparison. After vaccination, they will be followed for cytokine and chemokine responses as well as changes in the concentrations of estradiol and progesterone hormones.

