
Primary Objectives:

1. To explore whether receipt of IIV during the second week of the menstrual cycle (i.e., the week prior to ovulation) is associated with changes in steroid hormone levels, particularly decreases in progesterone, following ovulation.
2. To assess the feasibility of conducting further research in this area.

Primary Endpoints:

1. Changes in levels of estradiol and progesterone one week after receipt of influenza vaccination.

Exploratory Objectives:

1. To explore whether inflammatory cytokine responses to IIV receipt are associated with changes in reproductive hormone levels.
2. Identify optimal biomarkers of the inflammatory response after vaccination.
3. To collect peripheral blood mononuclear cells (PBMC) for future studies of cellular immune response.

Exploratory Endpoints:

1. Assess the inflammatory cytokine responses (including C-reactive protein [CRP]) to IIV.
2. To record adverse events in the 7 days after vaccination, including fever, myalgia, malaise, and hypersensitivity reactions.

II. Background and Rationale: Explain why this study is being done. Summarize briefly what is already known about the issue and reference previously published research, if relevant.

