Despite the decreases seen in IL-8 in non-pregnant adult men and women, two recent studies looking at inflammatory responses in pregnant women after influenza vaccination showed an increase in concentrations of IL-8, CRP, IL-6, TNF α , and MIF 48 hours after influenza vaccination [12, 13]. Discrepancies among studies might be caused by whether studies recruited women only [12, 13] or combined outcome data from both women and men [23]. No group has looked to see if these inflammatory responses after vaccination affect steroid hormone levels or if they have any effect on the earliest stages of pregnancy. This study is designed to explore these questions.

During our initial pilot study conducted during the 2013-2014 influenza season we examined the earliest immune responses to influenza vaccine and the potential impact on reproductive and stress hormones on women of reproductive age. Our initial findings showed no significant changes in serum hormone levels of estrogen, progesterone and cortisol after vaccination, compared with similar time points in a baseline menstrual cycle without vaccination. However, a non-significant 20% decrease in serum progesterone was observed after vaccination as compared to the non-vaccinated month[5]. Initial findings also showed increases in some cytokine levels after vaccination, compared with levels before vaccination during the vaccination menstrual cycle; cytokine levels were not assessed during the baseline menstrual cycle without vaccination[5]. Studying a larger number of women over 1 or 2 additional influenza seasons would help us better understand the effects of IIV on early immune responses and hormone levels.

III. Study Design:

A.

This is an open label study looking at the effect of influenza vaccine on cytokines and reproductive hormones. We will recruit women of reproductive age who are not on hormonal birth control, measure their cytokines and reproductive hormones for 1 month to establish a baseline, and then vaccinate them with the seasonal inactivated influenza vaccine just prior to ovulation, and follow the cytokines and reproductive hormones for the remainder of their cycle. We will use commercially available urine Luteinizing hormone (LH) strips to measure ovulation.

B. Provide a sample size and a justification as to how you arrived at that number. If you use screening procedures to arrive at a final sample a table may be helpful.

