1. Women 18-39 years of age who are in good health.

2. Good general health as a result of review of medical history and/or clinical testing at the time of screening.
3. Available for the duration of the trial.
4. Willingness to participate in the study as evidenced by signing the informed consent document.
5. Willing to be abstinent or to use non-hormonal methods of contraception for the duration of the study.
6. History of normal menstrual cycles (26 to <35 days in length) for ≥3 months prior to enrollment.
7. Willingness to refrain from routine vaccination (except as administered during study) for the duration of the study.

B. Exclusion Criteria:

1. Use of contraceptive pills, patch, injection or other hormonal therapies in the preceding 3 months. Or 6 months for Depo-Provera.
 2. A history of hypersensitivity, including anaphylaxis to any of the components of IIV or to eggs.
 3. Previous receipt of the same-season influenza vaccine.
 4. Pregnancy as determined by a positive urine or serum human chorionic gonadotropin (β-hCG) test at any point during the study or in the preceding 3 months.
 5. Currently is lactating or breast-feeding.
 6. Fewer than 3 normal menstrual cycles since conclusion of last pregnancy or last use of hormonal birth control.
 7. A history of autoimmune disease, or any other chronic medical condition considered clinically significant by the investigator.
 8. History of HIV, Hepatitis C or active Hepatitis B.
 9. Known immunodeficiency syndrome.
 10. History of Guillain-Barré syndrome.
 11. Use of chronic oral or intravenous administration (≥14 days) of immunosuppressive doses of steroids, i.e., prednisone >10 mg per day, immunosuppressants or other immune-modifying drugs within 30 days of starting this study. (Use of topical, nasal or inhaled steroids is permitted)
 12. Receipt of a live vaccine within 4 weeks or a killed vaccine within 2 weeks prior to study start or during study.
 13. Receipt of blood or blood-derived products (including immunoglobulin) within 6 months prior to study vaccination.
 14. Receipt of another investigational vaccine or drug within 30 days prior to study start, or during study.
 15. Ongoing, daily use of analgesics or anti-inflammatory medications, including nonsteroidal anti-inflammatories. Occasional use, and use associated with menstrual periods is acceptable.

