Country	Consent Document(s) (Adult Consent, Parental Permission, Youth Assent, etc.)	Languages
USA	Adult Informed Consent Form	English

Study Implementation:

1. Describe the procedures that participants will undergo. If complex, insert a table below to help the reviewer navigate.

		Month	screening	1						2						
Procedure	Blood volume	Day	-30 to -0	0	11	12	13	17	21	28	39	40	41	45	49	56
Complete History/ Physical			X													
Obtain Informed Consent			X													
Interim Clinical Evaluation				X	X			X	X	X	X	X	X	X	X	X
Urine pregnancy test			X	X							X					X
VACCINATION											X					
Progesterone/ estradiol	5			X	X			X	X	X	X			X	X	X
Cytokines (serum)	5				X	X	X				X	X	X			
HAI	5										X					X
PBMC	30				X				X		X				X	
Daily blood volume			0	5	40	5	5	5	35	5	45	5	5	5	35	10
Cumulative Total blood volume			0	5	45	50	55	65	95	100	145	150	155	160	195	205

2. Describe the number and type of study visits and/or contacts between the study team and the participant, how long they will last, and where/how they will take place.

Each subject will be expected to come to approximately 14 visits

Each participant will spend about 3-4 months in the study, from screening to completion

NOTE: At the investigator's discretion or if influenza is circulating in the community at the time of enrollment, the procedures of days 39-56 will be flipped with Day 11-28. In addition the two months of the study may not be continuous, for scheduling reasons, there may be 1-2 months in between.

Day 0 +/- 4 days (1st day of menstrual cycle)

1. Verify that study-specific Informed Consent was obtained.
2. Ensure that all inclusion/exclusion criteria are met.
3. Collect brief history of any new illnesses or problems since last visit
4. Review pregnancy prevention counseling.
5. Obtain blood for measurement of progesterone, and estradiol.
6. Train subjects on the REDCap survey website, or on memory card.
7. Instruct on LH strip use at home.

Day 10-17

1. Participant to utilize LH strip at home, and call study staff when positive.
2. Participant to record on memory card results of LH strip.

Day 11 +/-2 days (prior to ovulation),

1. Collect brief history of any new illnesses or problems since last visit
2. Review pregnancy prevention counseling.
3. Obtain blood for measurement of progesterone and estradiol and measurement of cytokines
4. Collect approximately 30 cc of blood for Peripheral Blood Mononuclear Cell (PBMC) processing.

Day 12, Day 13

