The data will be analyzed using the computer software STATA (version 13, Stata Corp, College Station, TX). Each participant will serve as her own control. Summary data of the baseline characteristics of participants will be described using mean (SD) and median for continuous variables or frequencies and proportions for categorical data, as appropriate. Vaccine HAI titers will be measured prior to vaccination (day 39) and at 17 days following vaccination (day 56)

PA1: To determine if vaccination with IIV prior to ovulation (day 11 of menstruation) is associated with changes in post-ovulation serum reproductive (progesterone and estradiol) hormone concentrations.

-H 1: Post-vaccination serum reproductive hormone concentrations will be lower in the post-vaccination cycle than measured prior to vaccination.

The skewness of the hormone concentration distributions will be checked using Kolmogorov-Smirnov test or Shapiro-Wilks test. Transformation of the non-normal data to achieve normality will be attempted using natural logarithms or other mathematical functions. In the event that power transformations fail to normalize the data then non-parametric tests will be used. The mean difference (SD) between pre-vaccination serum hormone (progesterone and estradiol) concentrations and post-vaccination serum hormone concentrations measured during the luteal phase (days 17, 21, 28) of menstruation for each participant will be estimated using paired t-test for parametric data or by the Wilcoxon matched-pairs signed rank sum test for non-parametric data. A p-value < 0.05 will be considered statistically significant in all analyses. Stratified analyses will be conducted to determine if host characteristics modify the effects of vaccination on hormonal responses.

EA1: To determine if serum inflammatory biomarker (cytokines, chemokines, and C-reactive protein) concentrations differ following vaccination with IIV.

-H2: Serum pro-inflammatory biomarker concentrations at 24- and 48-hours post vaccination will be increased relative to baseline concentrations.

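### The primary comparison treats Day 17 and Day 45 samples as post-ovulatory by calendar day, although cycles of 26 to 34 days are eligible and no written rule uses the recorded LH results

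*Protocol*

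**What the plan says.** The primary endpoint (Protocol, Primary Endpoints) is "Changes in levels of estradiol and progesterone one week after receipt of influenza vaccination". In the visit schedule this is the Day 45 draw, 6 to 8 days after vaccination. Its counterpart in the unvaccinated cycle is Day 17, which the schedule labels as after ovulation. The opening summary reports the pilot's 20% progesterone fall "as compared to the same menstrual cycle time point (day 17) in the non-vaccinated month".

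The aim (Protocol V, Study Implementation, item 4, PA1) is whether vaccination is "associated with changes in post-ovulation serum reproductive (progesterone and estradiol) hormone concentrations". The test under PA1 is a paired t-test or Wilcoxon signed-rank test on hormones "measured during the luteal phase (days 17, 21, 28) of menstruation for each participant". The only subgrouping planned is by unspecified host characteristics.

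Eligibility (Protocol IV.A, item 6) requires "History of normal menstrual cycles (26 to <35 days in length) for ≥3 months prior to enrollment", that is, lengths of 26 to 34 whole days.

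On ovulation, Protocol III.A says: "We will use commercially available urine Luteinizing hormone (LH) strips to measure ovulation". Strips are used on Days 10 to 17 and 38 to 45. The schedule says "Participant to record on memory card results of LH strip" and asks the participant to phone staff when a strip is positive. No text says what follows from that call. The SAP contains only the sample size text.

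**The concern.** The question is about hormone output after ovulation, but what qualifies a sample is the calendar. Progesterone rises after ovulation, so a Day 17 draw in a woman who has not yet ovulated does not measure luteal output. Three things can follow:

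- **Both samples before ovulation.** The pair cannot show a post-ovulation effect and pulls the estimate towards no change.
- **One sample before ovulation.** The pair adds a difference unrelated to luteal output, in a direction that depends on which cycle was late.
- **Vaccination delays ovulation.** Day 45 progesterone falls even if luteal output is unchanged. In a study motivated by vaccination in the week before ovulation, that is a different answer from reduced luteal output, and the planned paired test cannot tell the two apart.

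The data that would separate these cases are already being collected.

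**Working it through.** **Step 1: the plan's own figure.** Inputs from Protocol III.B and the SAP: n = 90, log10 SDs 0.51 and 0.54, correlation 0.60, alpha 0.05 (taken as two-sided).

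- SD of the difference = sqrt(0.51² + 0.54² − 2 × 0.60 × 0.51 × 0.54) = 0.470.
- Effect at ratio 0.75 = |log10 0.75| = 0.125.
- Paired t-test power (noncentral t) = 0.703. The plan states 0.69, so the power table is not in question.

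**Step 2: which cycle lengths are exposed.** Assumptions: the surge falls k days before the next menses (k = 15, range 13 to 17), ovulation is one day later, and days count from menses onset. For cycle length L, ovulation is on day L − k + 1, and a draw on day D is early if L − k + 1 > D.

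| k | early at nominal Day 17 | count of 9 |
|---|---|---|
| 13 | 30–34 | 5 |
| 14 | 31–34 | 4 |
| 15 | 32–34 | 3 |
| 16 | 33–34 | 2 |
| 17 | 34 | 1 |

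The Day 17 visit has a window of ±2 days. At k = 15, a Day 15 draw is early for 30–34 (5 of 9) and a Day 19 draw only for 34 (1 of 9). A nominal Day 21 draw is early for no eligible length at k = 15 and for one (34) at k = 13, so the later draws are less exposed.

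The two draws of a pair need not fall on the same cycle day. Vaccination on Day 39 ± 3 is about cycle day 8 to 14, and 6 to 8 days later is cycle day 14 to 22, against 15 to 19 in the unvaccinated cycle.

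**Step 3: delayed ovulation.** Suppose vaccination delays ovulation by 2 days (assumption), with k = 15. A nominal Day 45 draw (cycle day 17) is then early when L − 15 + 1 + 2 > 17, that is for 30–34 (5 of 9), against 3 of 9 in the unvaccinated cycle. The lengths 30 and 31 become mixed pairs, low in the vaccinated cycle.

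**Step 4: possible effect on the estimate (illustrative shares).** If a share p of pairs is early in both cycles and shows no change, the effect is 0.125 × (1 − p). At p = 5%, 10% and 20%, a true ratio of 0.75 is estimated as 0.76, 0.77 and 0.79, and all-pairs power is 0.66, 0.61 and 0.51.

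For mixed pairs, take a net 5 of 90 with only the vaccinated-cycle sample early, each lower by one pilot SD (0.51). The shift is 5 × 0.51 / 90 = 0.028, or 23% of 0.125. For drops of 0.3 to 1.0 log10 it is 13% to 44%.

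**Step 5: does an LH-confirmed set gain power?** Removing exactly the affected pairs leaves 86, 81 or 72, with power 0.68, 0.66 or 0.60 at a true ratio of 0.75. A workable rule, drawn 2 or more days after the first positive, removes more: Day 17 is unconfirmed when L − k + 2 > 17, which at k = 15 is 31–34 (4 of 9, not 3), and one extra length at every k from 13 to 17.

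To match the all-pairs test, the confirmed set needs 82 pairs at p = 5% and 74 at p = 10%. That allows only 4 and 7 further losses (86 − 82, 81 − 74). If the 30 pilot women have no LH dates, at most 60 pairs remain (power 0.53). After the same 5%, 10% and 20% removals, 57, 54 or 48 remain (power 0.50, 0.48, 0.44), below the diluted all-pairs figures.

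**Step 6: end of strip testing.** Strips stop on Day 17/45. The surge is later than that (L − k > 17) for 33–34 at k = 15 (2 of 9), and for 4 to 0 of 9 over k = 13 to 17.

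**The case against.** The strongest reply is that the schedule intends LH-guided timing: the Day 17 visit is labelled as after ovulation, has a ±2 day window, and participants phone in a positive strip. That is a fair reading of intent. But no rule moves a draw, and Day 45 is tied to the vaccination date rather than to the surge. The statement in item 5.E that strips will not guide clinical action does not prevent their use in analysis.

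Second, the endpoint as worded is a change one week after vaccination, not conditioned on ovulation, and the objectives are exploratory. The all-pairs test does answer that wording, which is why it should stay. It does not by itself answer the post-ovulation aim.

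Third, the inputs are soft. The shares of 5% to 20% and the five net pairs have no source in the documents. The power inputs describe the luteal phase generally. If the pilot followed the same schedule, its ratio may already include early pairs, so diluting 0.75 again could double-count. All of this stands, and the figures in Step 4 only illustrate scale.

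A reader might infer that restricting to LH-confirmed pairs would restore lost power. Step 5 does not support that. A reader might also infer that a third of women would be sampled too early. The count is of cycle lengths, not women, and the documents give no distribution of lengths.

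**Conclusion.** The concern holds as one of bias and interpretation. The plan collects LH results but, as written, pools any pre-ovulatory Day 17 or Day 45 sample with luteal ones and cannot distinguish delayed ovulation from lower luteal progesterone. At least one eligible cycle length is exposed at nominal Day 17 under every surge timing tried: 3 of 9 centrally, 5 to 1 over the range. This rests on the assumed interval from surge to menses and on counting days from menses onset. The number of women affected, and the net direction of any shift, cannot be derived from the documents.

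It would go too far to conclude that the pilot's progesterone fall was a timing artefact, or that the planned primary test is invalid. The documents give no LH data from the pilot and no share of early samples, and the power table reproduces.

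**What to change.** Add to the PA1 analysis:

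1. Keep the all-pairs paired test as planned.
2. Add one sensitivity analysis limited to pairs in which both the Day 17 and the Day 45 sample were drawn 2 or more days after that cycle's first positive LH strip. Do not use progesterone to select samples, because it is the outcome.
3. Report the number of unconfirmed samples in the vaccinated and the unvaccinated cycle.
4. Compare the day of first positive strip between the two cycles.

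Optionally, continue strips past Day 17/45 until positive. Reaching the latest assumed surge (34 − 13 = Day 21) takes up to 4 more strips per cycle.

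The cost is a few sentences, since strip results are already recorded. There are two limits to state. The confirmed set conditions on an event after vaccination, so it should remain a sensitivity analysis. It also loses pairs, and the documents do not say whether the 30 pilot women have LH dates; the plan should say so.

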1. Obtain blood for measurement of cytokines.

Day 17 +/-2 days (after ovulation), Day 21 +/- 2 days

Day 28 +/- 5 days (1st day of menstrual cycle)

1. Collect brief history of any new illnesses or problems since last visit
2. Review pregnancy prevention counseling.
3. Obtain blood for measurement of progesterone, and estradiol.

Day 21 +/- 2 days:

1. Collect approximately 30 cc of blood for PBMC processing.

Day 38-45

1. Participant to utilize LH strip at home, and call study staff when positive.
2. Participant to record on memory card results of LH strip.

Day 39 +/- 3 days (~ 11 days after menstruation; prior to ovulation)

1. Collect brief history of any new illnesses or problems since last visit
2. Review pregnancy prevention counseling.
3. Obtain blood for measurement of progesterone, estradiol, baseline cytokines and Hemagglutination Inhibition Assay (HAI).
4. Obtain approximately 30 cc of blood for PBMC processing.
5. Check urine pregnancy test.
6. Vaccinate subject with IIV.

Day 40 +/-1 day (1 day after vaccination), Day 41 +/-1 day (2 days after vaccination)

1. Collect brief history of any new illnesses or problems since last visit, ask about adverse events after vaccination.
2. Review pregnancy prevention counseling.
3. Obtain blood for measurement of cytokines.
Days 41-43 (2-4 days after vaccination).

Subject to answer questions reactivity in the REDCap database or on the memory card.

Day 45 +/-1 day (6-8 days after vaccination), Day 49 +/- 1 day (10-12 days after vaccination)

1. Collect brief history of any new illnesses or problems since last visit; ask about adverse events after vaccination.
2. Review pregnancy prevention counseling.
3. Obtain blood for measurement of progesterone, and estradiol.

Day 49 +/- 1 day (10-12 days after vaccination)

1. Obtain approximately 30 cc for PBMC processing.

Day 56 +/-4 days (1st day of menstruation)

1. Get brief history of any new illnesses or problems since last visit.
 2. Check urine pregnancy test.
 3. Obtain blood for measurement of progesterone, estradiol and for HAI.
3. Describe the expected duration of the study from the perspective of the individual participant and duration overall.

Each participant will spend about 3-4 months in the study, from screening to completion.
Each subject will be expected to come to approximately 14 visits

4. Provide a brief data analysis plan and a description of variables to be derived.

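### Read literally, the cycle swap leaves vaccine-first women with no pregnancy test during or after the unvaccinated cycle, so pregnancy detection depends on cycle order; the likely bias is small and the remedy cheap

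*Protocol*

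**What the plan says.** The row "Urine pregnancy test" in the schedule table (Protocol, section V, Study Implementation) is marked at screening and on Days 0, 39 and 56. The visit lists below it include the step "Check urine pregnancy test" on Days 39 and 56 only; the Day 0 list omits the test that the table marks.

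The NOTE after the table allows the vaccinated cycle to come first, at the investigator's discretion or when influenza is circulating. In that case "the procedures of days 39-56 will be flipped with Day 11-28". No procedure is exempted. The same NOTE says of the two study months that "there may be 1-2 months in between", and adds no test for that gap.

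Exclusion criterion 4 (section IV.B) begins "Pregnancy as determined by a positive urine or serum human chorionic gonadotropin" and applies at any time in the study, so it rests on a positive test. The closing visits are "Day 28 +/- 5 days (1st day of menstrual cycle" and "Day 56 +/-4 days (1st day of menstruation". Inclusion criterion 6 (section IV.A) requires "History of normal menstrual cycles (26 to <35 days in length"; criterion 5 requires abstinence or non-hormonal contraception.

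The data analysis plan compares luteal hormone values (Days 17, 21 and 28 and their counterparts) within each woman. It gives no rule for a cycle in which pregnancy occurs or menses does not follow. The SAP contains only the power statement and is silent on this.

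**The concern.** The design uses each woman as her own control, so it needs the same eligibility check on both cycles. In the usual order it has one: the Day 39 test comes after the unvaccinated cycle and the Day 56 test closes the vaccinated cycle. In vaccine-first women the Day 28 test closes the vaccinated cycle, and nothing closes the unvaccinated one. A pregnancy in the vaccinated cycle can be found and excluded; one in the comparison cycle can stay in.

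The direction is not neutral. The Protocol's opening summary states that estradiol and progesterone rise substantially in pregnancy. A retained pregnancy in the unvaccinated cycle would raise the comparator and make the vaccinated cycle look lower, which is the direction of H1. The swap is partly discretionary and the documents set no limit on how many women it may affect.

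**Working it through.** **1. Applying the swap to the table.** The NOTE maps Days 11, 12, 13, 17, 21, 28 onto 39, 40, 41, 45, 49, 56 and back. Screening and Day 0 are outside it.

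| Order | Unvaccinated cycle | Tests after screening | First test after the unvaccinated cycle |
|---|---|---|---|
| Usual | Days 0-28 | 0, 39, 56 | Day 39 |
| Vaccine-first | Days 28-56 | 0, 11, 28 | none |

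With consecutive cycles the swapped Day 28 test falls on the opening day of the unvaccinated cycle and clears its start. After a gap of 1-2 months it does not.

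**2. Does the closing visit confirm menses?** Day 56 + 4 = Day 60, which is 60 - 28 = 32 days after a nominal Day 28. If the Day 28 window of +/-5 travels with the swap, the limit is 33 days. Eligible cycles run to 34 days, so on either count the visit can precede menses. Because Day 28 itself floats, the permitted distance between the two visits is 52 - 33 = 19 to 60 - 23 = 37 days. The window therefore neither guarantees nor rules out that menses has begun.

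**3. The plan's own power figure.** Inputs from Protocol section III.B and the SAP: SDs 0.51 and 0.54 (log10), correlation 0.60, n = 90, alpha 0.05.

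- SD of the difference = sqrt(0.51² + 0.54² - 2 × 0.60 × 0.51 × 0.54) = 0.470.
- Standard error = 0.470/sqrt(90) = 0.0496.
- For a median ratio of 0.75, |log10 0.75| = 0.125. Two-sided paired-t power is 0.703, against 0.69 in the table.

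That is close enough to use this standard error as the yardstick.

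**4. Bias per retained pregnancy.** Let k women of 90 have an undetected pregnancy in the unvaccinated cycle, each raising that cycle's log10 progesterone by x. Then bias = -k × x/90. The documents give no x; I assume 0.3 to 1.5 (about 2-fold to 30-fold). For k = 1:

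| x | Shift (log10) | Share of -0.13 | Share of SE 0.0496 |
|---|---|---|---|
| 0.3 | -0.0033 | 2.6% | 0.07 |
| 1.0 | -0.0111 | 8.5% | 0.22 |
| 1.5 | -0.0167 | 12.8% | 0.34 |

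If only the Day 28 sample were raised and log values were averaged over the three luteal days, each shift would be a third as large. For x = 1.0 to 1.5 that is -0.0037 to -0.0056, or about 3-4% of -0.13.

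**5. How many cases?** The documents give neither the number of vaccine-first women nor a pregnancy rate. Assuming 20-80% of the 90 are vaccine-first and 0.5-2% conceive per cycle, the expected number runs from 90 × 0.20 × 0.005 = 0.09 to 90 × 0.80 × 0.02 = 1.44. In the worst corner the shift is 1.44 × 1.5/90 = 0.024, about 18% of 0.13 and about half a standard error.

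**6. Could bias alone reach significance?** The smallest significant mean difference is about 0.0985 log10 (ratio 0.80). With the SD held fixed, reaching it takes 0.0985 × 90/x: about 30 pregnancies at x = 0.3, 9 at x = 1.0, or 6 at x = 1.5.

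**The case against.** Several points on the other side stand.

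- A reader might infer that the swap moves the in-study tests into the vaccinated cycle. The documents do not support this. The Day 39 and Day 56 tests accompany vaccination in both orders, and the table also marks Day 0. What is lost is a later test that covers the unvaccinated cycle.
- A reader might also object that about 95 mL (40+5+5+5+35+5) is drawn from vaccine-first women in an untested cycle. This does not separate the orders: in the usual order the same volume is drawn on Days 11-28 with no test between Day 0 and Day 39.
- The primary endpoint in section I is one week after vaccination. Nothing in the documents shows that a pregnancy-related rise reaches the corresponding sample (Day 17 or 45), so for that time point the bias could be much smaller.
- Contraception or abstinence is required and counselling is repeated. Absent menses at a visit labelled as the first day of menstruation would be noticed, and a large hormone elevation would show in the trial's own assays.
- Exclusion 4 accepts a urine or serum test at any time, and leftover serum is kept, so an unscheduled test is possible.

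These points reduce the size of the problem without removing it. No scheduled step prompts a test when menses is absent, and no rule says what to do with such a cycle. Finding a pregnancy from an outlying hormone value would mean deciding on exclusion after seeing the outcome, in a study where staff are not blinded.

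**Conclusion.** The gap is real and follows from the table and the NOTE read together: vaccine-first women have no scheduled pregnancy test during or after the unvaccinated cycle, and none before it when the cycles are separated. For that cycle exclusion 4 cannot be applied from any scheduled test, and the visit window does not guarantee that menses has begun. Any resulting bias runs towards H1.

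Its size is modest: about 3-13% of -0.13 per case and under 0.35 of a standard error, with roughly 0.1 to 1.4 cases expected. The elevation, the pregnancy rate and the vaccine-first share are all assumptions. A reader might go further and infer that an undetected pregnancy would pass for a vaccine effect; the figures do not support that, since it would take at least about six such pregnancies even at the largest assumed elevation. No sample size or power figure changes. The point deserves action because detection should not depend on cycle order and the repair is cheap.

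**What to change.** - Amend the NOTE so that a urine pregnancy test is kept at the closing visit of the unvaccinated cycle in both orders, and at the start of the second cycle after a gap, in addition to the tests that accompany vaccination.
- Reconcile the Day 0 visit list, which omits the test, with the table, which marks it.
- Add one sentence to the analysis plan: cycles with a positive test, or with neither confirmed menses nor a negative test at the closing visit, are handled identically in the paired comparison whether vaccinated or unvaccinated. Fix this rule before the hormone data are examined.

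The cost is one or two extra urine kits per vaccine-first woman, of a type already used in the trial and at visits already scheduled, plus a short amendment. The same closing-visit wording also adds a kit at Day 28 in the usual order.
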